explanation that the subject may receive no direct benefit from participating but patient care may in general improve if the study drug successfully prevents delirium. If the patient is interested in enrolling then the patient is asked to remember 3 words (apple, penny, and table) and then is distracted by being asked to recite the days of the week backwards starting with Sunday. If the subject can remember at least 2 of the 3 words then the entire consent is reviewed in depth and the subject is asked if he understands and if he has any questions before signing. A “teach back” will be accomplished to insure that the subject or the surrogate understands all the research aspects of the study. A Short CAM will then be performed by the investigator to evaluate for delirium. If delirium is not diagnosed via the Short CAM, the consent form will be completed and the patient entered into the trial.

9. **Risks:** Describe the reasonably foreseeable risks, including risks to subject privacy, discomforts, or inconveniences associated with subjects participating in the research.

Minimal risks are anticipated with this study however participation in the study may involve risks that are currently not known. Possible risks include the swallowing of an extra pill and the lack of ability to take melatonin for impaired sleep. While Micromedex lists side effects of melatonin, such as tachyarrhythmia, red/flushed skin, hypothermia, decreased glucose tolerance, abdominal cramps/diarrhea, confusion, decreased reaction time, sedation, sleep pattern disturbance, and worsening of depression, these are considered rare and usually with little clinical effect. A recent review in the journal *Clinical Drug Investigations* (Andersen LP, Gögenur I, Rosenberg J, Reiter RJ. *Clin Drug Investig.* 2016 Mar;36(3):169-75. doi: 10.1007/s40261-015-0368-5. PMID:26692007) concluded that the short-term use of melatonin is safe, even in extreme doses and that only mild adverse effects have been reported and are probably no different than placebo²⁹, with the possible exception of sleepiness. Other potential adverse effects include dizziness, headache, and nausea as described below, in section VI.2. Melatonin should have no major drug interactions or effects on other possible drug interventions in our subjects. Mild to moderate interactions with warfarin, nifedipine and fluvoxamine are noted in Micromedex and patients treated with these medications will not be included in the study.

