The principal investigator is responsible for monitoring the data, assuring protocol compliance, and conducting the safety reviews at the specified frequency on a monthly basis. During the review process the principal investigator will evaluate whether the study should continue unchanged, require modification/amendment, or close to enrollment.

The principal investigator or the Institutional Review Board (IRB) have the authority to stop or suspend the study or require modifications.

This protocol presents minimal risks to the subjects and adverse events or other problems are not anticipated. In the unlikely event that such events occur, Reportable Adverse Events (which are events that are serious or life-threatening and unanticipated (or anticipated but occurring with a greater frequency than expected) and possibly, probably, or definitely related) or unanticipated problems involving risks to subjects or others will be reported in writing within 48 hours to

the IRB (using the appropriate forms from the website) and any appropriate funding and regulatory agencies. The investigator will apprise fellow investigators and study personnel of all adverse events that occur during the conduct of this research project through regular study meetings.

- d. For multi-site studies for which the Yale PI serves as the lead investigator:
- i. How will adverse events and unanticipated problems involving risks to subjects or others be reported, reviewed and managed?
 - ii. What provisions are in place for management of interim results?
 - iii. What will the multi-site process be for protocol modifications?

12. **Statistical Considerations:** Describe the statistical analyses that support the study design.
13.

Primary Outcome:

Incidence of delirium per admission of medical geriatric patients

Incidence of delirium per patient days of hospitalization in medical admission of geriatric patients

Secondary outcomes:

Risk factors associated with incident delirium

Duration of delirium by study group

Hospital length of stay

Sample size based was estimated using openepi.com (similar results with Stata version 14 sample size calculator) based on control group incidence of delirium in medical subgroup of 30%. (Chen et al: Exogenous melatonin for delirium prevention: a meta-analysis of randomized controlled trials - Molecular Neurobiology online publication 21 July 2015) with relative risk reduction of 30 %.

Sample Size: X-Sectional, Cohort, & Randomized Clinical Trials

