- ii. The diagnostic test is intended to be used in a diagnostic procedure that confirms the diagnosis made by another, medically established, diagnostic product or procedure; and
- iii. The diagnostic test is shipped in compliance with 21 CFR §312.160.

Exempt Category 3

- The drug is intended solely for tests in vitro or in laboratory research animals if shipped in accordance with 21 CFR 312.60

Exempt Category 4

- A clinical investigation involving use of a placebo if the investigation does not otherwise require submission of an IND.

- 2. **Background Information:** Provide a description of previous human use, known risks, and data addressing dosage(s), interval(s), route(s) of administration, and any other factors that might

influence risks. If this is the first time this drug is being administered to humans, include relevant data on animal models.

Melatonin is categorized by the FDA as a dietary supplement and is currently in use over the counter and ordered in a small percentage of hospitalized patients as a sleep aid. Side effects of melatonin are rare and mild; documented adverse effects to melatonin include dizziness, headache, nausea, and sleepiness. With the exception of sleepiness these are similar in incidence to placebo. The half-life of melatonin is 30 to 50 minutes. There have been no studies to date that have documented any serious adverse effects related to short or even long term use of melatonin.²⁹ Melatonin is taken orally. Because it is categorized as a dietary supplement and not a drug, it is marketed over the counter, and there is no recommended dose. It is marketed in doses ranging from 0.5 to 10 mg. See section 9, Risks, for all the possible side effects as listed in Micromedex.

3. **Source:** a) Identify the source of the drug or biologic to be used.

The Yale Investigational Drug Service Pharmacy

b) Is the drug provided free of charge to subjects? Yes No
If yes, by whom?

Per the Department of Medicine Research Grant funding

3. **Storage, Preparation and Use:** Describe the method of storage, preparation, stability information, and for parenteral products, method of sterilization and method of testing sterility and pyrogenicity.

No special storage or preparation will be required.

Check applicable Investigational Drug Service utilized:

YNHH IDS

CMHC Pharmacy

PET Center

Other:

Yale Cancer Center

West Haven VA

None

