If yes, describe the nature of this relationship.

Several members of the research team may be working as either the resident or attending physician for the study subjects at the time of data collection. The Yale Investigational Drug Service will be doing the randomization so that all will remain blinded as to the treatment arm and the placebo arm.

6. Request for waiver of HIPAA authorization: (When requesting a waiver of HIPAA Authorization for either the entire study, or for recruitment purposes only. Note: if you are collecting PHI as part of a phone or email screen, you must request a HIPAA waiver for recruitment purposes.)

Choose one:

- For entire study
- For recruitment purposes only
- For inclusion of non-English speaking subject if short form is being used

- i. Describe why it would be impracticable to obtain the subject's authorization for use/disclosure of this data; The patients' names who are admitted to Celantano 3, Celantano 4, Verdi 5 North, and Verdi 4 West and fit our inclusion criteria will be sent to the investigators via OnCore / EPIC. Before interviewing the patient we will need to review our exclusion criteria which can be done both via EPIC chart review and with discussion with the primary team. Once we are comfortable

that the patient is a candidate for inclusion we will interview the patient and further review the inclusion and exclusion criteria and begin the invitation to consider participating in the study. By reviewing the chart and perhaps interviewing the care team we will avoid needlessly bothering some patients and be more efficient in our recruitment process.

- ii. If requesting a waiver of **signed** authorization, describe why it would be impracticable to obtain the subject's signed authorization for use/disclosure of this data; In the event that a patient does not understand and/or cannot explain back to the investigator seeking informed consent, what the study entails, but does give us his/her affirmative assent, we will seek out the LAR, in person or by phone, to obtain a surrogate consent.

By signing this protocol application, the investigator assures that the protected health information for which a Waiver of Authorization has been requested will not be reused or disclosed to any person or entity other than those listed in this application, except as required by law, for authorized oversight of this research study, or as specifically approved for use in another study by an IRB.

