Yes *If you answered yes, stop. A waiver cannot be granted.* Please note: Recruitment/screening is generally a minimal risk research activity

No

b. Will the waiver adversely affect subjects' rights and welfare? Yes No

c. Why would the research be impracticable to conduct without the waiver? The patients' names who are admitted to Celantano 3, Celantano 4, Verdi 5 West and Verdi 4 West and fit our inclusion criteria will be sent to the investigators via OnCore / EPIC. Before interviewing the patient we will need to review our exclusion criteria which can be done both via EPIC chart review and with discussion with the primary team. Once we are comfortable that the patient is a candidate for inclusion we will interview the patient and further review the inclusion and exclusion criteria and begin the invitation to consider participating in the study. By reviewing the chart and perhaps interviewing the care team we will avoid needlessly bothering some patients and be more efficient in our recruitment process.

d. Where appropriate, how will pertinent information be returned to, or shared with subjects at a later date? N/A

Requesting a full waiver of consent for the Entire Study (Note: If PHI is collected, information here must match Section VII, question 6.) N/A

If requesting a full waiver of consent, please address the following:

a. Does the research pose greater than minimal risk to subjects?

Yes *If you answered yes, stop. A waiver cannot be granted.*

No

b. Will the waiver adversely affect subjects' rights and welfare? Yes No

c. Why would the research be impracticable to conduct without the waiver?

d. Where appropriate, how will pertinent information be returned to, or shared with subjects at a later date?

SECTION VIII: PROTECTION OF RESEARCH SUBJECTS

Confidentiality & Security of Data:

a. What protected health information (medical information along with the HIPAA identifiers) about subjects will be collected and used for the research?

- Medical record number
- Date of Admission
- hyperactive delirium
- hypoactive delirium
- Length of stay
- Age
- Gender
- Primary diagnosis
- Secondary diagnosis
- Mortality
- Use of restraints
- # prn antipsychotic doses
- PRN sleep meds
- Placement of foley catheter
- Result of daily CAM assessment

b. How will the research data be collected, recorded and stored?

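### The safety rule turns on events being more frequent than expected, but the plan states no expected rate, no structured adverse-event count and no by-arm table of harms

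*Combined protocol and SAP*

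**What the plan says.** **The rule.** Section V.11 (Data and Safety Monitoring Plan) requires a written report within 48 hours for an event that is serious or life-threatening, at least possibly related, and either unanticipated or "anticipated but occurring with a greater frequency than expected".

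**Who reviews.** The principal investigator is charged with "conducting the safety reviews at the specified frequency on a monthly basis" and decides whether the study continues, changes or closes. The IRB shares the power to stop: "The principal investigator or the Institutional Review Board (IRB) have the authority to stop or suspend the study". Under Section VII.5 the Investigational Drug Service randomizes "so that all will remain blinded as to the treatment arm and the placebo arm".

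**What is expected.** Section V.9 (Risks) lists effects that include tachyarrhythmia, hypothermia, confusion and sedation, and says "these are considered rare and usually with little clinical effect". Section VI.A.2 names dizziness, headache, nausea and sleepiness and adds "With the exception of sleepiness these are similar in incidence to placebo". No rate is given. Section V.11 also says that adverse events are not anticipated.

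**What is recorded.** Section VIII, item a, lists 15 items. They include mortality, hyperactive and hypoactive delirium, restraints, as-needed antipsychotic doses and "Result of daily CAM assessment". None is an adverse-event, seriousness or relatedness field. Section V.10 has the team review every patient twice a day and follow complications. Section VI.A.4 has complications noted. Section V.11 has all adverse events shared at study meetings. No form, field or denominator is described.

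**What is analysed.** The outcomes and methods in Section V.12 concern delirium and length of stay. No harm is compared by arm, at the 367-subject analysis or at the end.

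**The concern.** A rule that reacts to a frequency needs three things: a count, a denominator and a reference value. Only the denominator can be had from the plan as written. Whether an anticipated serious event has become too frequent would then rest on impression.

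The larger loss comes at the end of the trial. This is a preventive drug, and on the plan's own 30% control rate about 70% of untreated patients would not become delirious. For them any harm has no offsetting benefit on the primary endpoint, so the reader of the final report needs a comparison of harms. Events that were noted but never entered in a defined field are hard to rebuild afterwards, and Section VIII, item e, plans to delete all subject data from the server once the research is complete.

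**Working it through.** **1. The plan's own figure.** The safety plan has no number of its own, so the sample size sets the denominators. Inputs from Section V.12: 30% against 21%, two-sided 5%, 80% power, 1:1. Fleiss without continuity correction:

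n = [1.960·√(2 × 0.255 × 0.745) + 0.842·√(0.30 × 0.70 + 0.21 × 0.79)]² / 0.09² = 367 per arm, 734 in total. This matches the plan.

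**2. What each part of the rule needs.**

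| Needed | What the documents give |
|---|---|
| Count of anticipated events | Complications followed, noted and discussed; no field or form |
| Seriousness and relatedness | Used in the rule; not on the data list |
| Expected frequency | Rare; similar to placebo except for sleepiness |
| Comparison by arm | None planned |

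**3. Illustration.** The documents give no event rates, so every rate here is an assumption. Take 5% on placebo and 10% on melatonin.

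- By arm: 367 × 0.05 ≈ 18 and 367 × 0.10 ≈ 37. Two-sided Fisher p = 0.011. The risk difference is 19/367 = 5.2 points. Its standard error is √[(0.101 × 0.899 + 0.049 × 0.951)/367] = 1.93 points, so the 95% interval is about 1.4 to 9.0 points.
- Pooled: (18 + 37)/734 = 7.5%. Against a known expected 5%, the one-sided exact binomial p is 0.002. So a blinded reviewer could flag this excess if the 5% were stated and the events were counted.

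**4. What pooled counts can and cannot do.** A doubling in one of two equal arms multiplies the pooled rate by (1 + 2)/2 = 1.5. The table gives the chance of a flag at 367 per arm, by one-sided 2.5% exact tests, with the expected rate assumed to be known exactly and equal to the placebo rate.

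| Placebo vs melatonin | Pooled, blinded | By arm |
|---|---|---|
| 1% vs 2% | 22% | 12% |
| 1% vs 3% | 61% | 40% |
| 5% vs 10% | 78% | 69% |
| 10% vs 20% | 98% | 96% |

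The pooled column depends wholly on the expected rate being right. With 5% assumed, a true background of 7.5% in both arms and no drug effect raises the flag 78% of the time, just as a true doubling does. If the background is really 5%/1.5 = 3.3%, a doubling on melatonin gives a pooled rate of 5%, and the chance of a flag falls to about 2%.

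**5. Rare events.** With 4 against 11 of 367, nearly a tripling, Fisher p = 0.11. The difference is 7/367 = 1.9 points, with a 95% interval of about −0.1 to 3.9 points. For such events the use of a by-arm table is the estimate and its interval, not a test.

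**The case against.** Several points on the other side stand.

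- **The rule does not compare arms.** It covers serious, at least possibly related events and sets their frequency against an expectation. A reader might infer that blinding the investigator disables it, or that an excess on melatonin could never be seen. The documents do not support either. Step 4 shows that pooled counts can reveal an excess when the expected rate is known. The limb for unanticipated events needs no rate at all.
- **The data list is not shown to be the whole case report form.** It answers a question about protected health information, and it omits items that the analysis needs, such as comorbidities and number of medications. Absence from it does not prove that an item goes uncollected. It is, however, the only list in the documents, and no other place describes how an adverse event is recorded.
- **Some safety data are there.** Mortality is listed, and confusion is partly covered by the CAM and delirium items. Deaths could be tabulated by arm from listed data, so it would be wrong to say that the report could give no comparative harm.
- **The illustration is generous.** The documents call the known effects rare and mostly mild, so few would reach the serious limb.
- **Proportionality.** The protocol classes the study as minimal risk. A monthly unblinded review might seem to follow from the gap, but it does not. The independent statistician's stated task is tied to the analysis of 367 subjects, so monthly tables would be a new role, and repeated looks at several events without a threshold would raise false alarms.

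None of this supplies an expected rate, a structured count or a planned comparison of harms.

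**Conclusion.** The point holds as a gap in capture, reference value and analysis. As written, the frequency limb of the reporting rule cannot be applied reliably to anticipated events. An excess that was noticed could not be attributed to melatonin. The final report could compare little beyond deaths and delirium-related items.

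The size cannot be fixed from the documents, because they give no event rates. Under the assumed rates in the working, pooled monitoring would flag a doubling or tripling with a chance of 22% to 98% at full enrolment if the expected rate were known and events were counted. For a doubling the chance falls to about 2% if the true background is 1.5 times lower than assumed.

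The conclusion assumes that no fuller case report form or safety table exists outside the documents; if one does, it should be cited. The primary efficacy analysis is not affected. This should be corrected, but it does not undermine the design.

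**What to change.** 1. **Section VIII, item a.** Add dated yes/no fields for the adverse events that the protocol names in Sections V.9 and VI.A.2, and one for any other serious event, with seriousness and relatedness. Fill them from the twice-daily review in Section V.10.
2. **Section V.11.** State the reference frequency against which pooled counts are compared, with its source, and reconcile the statement that adverse events are not anticipated with the list in Section V.9.
3. **Section V.12.** Add a by-arm table of these events and of deaths, with risk differences and 95% confidence intervals, at the final analysis. If an interim version is wanted, the independent statistician can prepare it at the 367-subject analysis already planned, so that the investigators stay blinded.

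The cost is some chart-abstraction time and one more table. No patient procedure is added. If the interim version is chosen, the plan must also say that the statistician receives the arm codes, which it does not state now.

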Within 24 hours of admission to the inpatient floor, study subjects will be approached by a member of the research team, and asked for informed consent. Patients that consent to participate and meet our inclusion criteria will be ordered the appropriate study drug by the floor pharmacist, per the Yale Investigative Drug Service's randomization to either the treatment or the placebo arm. Each subject will be ordered a capsule containing either placebo (cellulose microcrystalline) or 5 mg melatonin each evening at 9 p.m. The study drug can be given as early as 7pm on the day of admission, if necessary, to allow treatment to begin within 24 hours of admission to the floor.. The capsules will be prepared and administered by the Yale-New haven Hospital Investigational Drug Service. The capsules will be administered nightly until discharge or a maximum of 2 weeks if the hospitalization is prolonged. The capsule must be swallowed whole and not opened.

Subjects will be assessed twice daily, once in the- a.m. and again in the p.m by the floor nurses for evidence of delirium using the Short CAM (Confusion Assessment Method), which is a validated clinical tool for identifying delirium, and the current standard of practice tool for the diagnosis of delirium. This evaluation should take maximally 5 to 10 minutes to complete.

While it is considered standard of care for nurses to administer the Short CAM once daily at Yale-New Haven Hospital, the twice daily Short CAM is standard of care at the University of Connecticut Hospital but not currently at the Yale-New Haven Health System with the exception of Verdi 4 West where the CAM is administered twice a day for all patients.

The primary endpoint will be the occurrence of delirium as defined by the Short CAM by the time of discharge or prior to hospital day 15, whichever occurs first. The study drug will be continued until the primary end point of delirium is reached, discharge or hospital day 15.

The maximum period of study drug administration will be 14 days. If the patient's length of stay exceeds 14 days the patient's participation in the study will end and the subject will be recorded as having completed the study without delirium. If the primary end point of delirium is reached, the subject will have completed the study, participation will be over and the study drug will no longer be administered.

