Two-sided significance level(1-alpha):	95
Power(1-beta, % chance of detecting):	80
Ratio of sample size, Unexposed/Exposed:	1
Percent of Unexposed with Outcome:	30
Percent of Exposed with Outcome:	21
Risk/Prevalence Ratio:	0.7
Risk/Prevalence difference:	-9

Sample size estimation by the Fleiss method yielded a total sample size of 734 with 367 in each group.

Descriptive statistics such as percentages for binary categorical variables, means and standard deviations for continuous variables. Fisher's exact test or chi-square test will be used to compare categorical variables. For continuous variables we will use t-test of unequal variances for means for normally distributed variables and the Wilcoxon-Mann-Whitney where normal distribution cannot be assumed. Risk ratio will be calculated using Stata statistical program version 14. (StataCorp LP, [name]) Associations with covariates will be tested using logistic regression with presence of incident delirium as the dependent variable.

Person days to delirium will be compared between the two groups using Survival analysis with Kaplan Meier curves, logrank test and Cox proportional hazards (covariates include age, comorbidities, medication numbers, presence of risk factors for delirium – polypharmacy, use of psychotropic or sedating medications, and use of bladder catheters).

Upon completing enrollment and analysis of 367 subjects, [name], a independent statistical expert, will analyze the data. In addition, an independent geriatrician expert in delirium will review any equivocal CAM results and make a decision as to the occurrence of delirium.

SECTION VI: RESEARCH INVOLVING DRUGS, BIOLOGICS, RADIOTRACERS, PLACEBOS AND DEVICES

If this section (or one of its parts, A or B) is not applicable, state N/A and delete the rest of the section.

A. DRUGS, BIOLOGICS and RADIOTRACERS

1. **Identification of Drug, Biologic or Radiotracer:** What is (are) the **name(s)** of the drug(s) biologic(s) or radiotracer(s) being used? Identify whether FDA approval has been granted and for what indication(s).

Melatonin—FDA categorized as a dietary supplement for sleep aid

All protocols which utilize a drug, biologic or radiotracer **not** approved by, but regulated by, the FDA, or a radiotracer regulated by the RDRC, must provide the following information:

a. What is the Investigational New Drug (IND) **number** assigned by the FDA?

FDA IND 129224-Melatonin

b. Who holds the IND?

[name]

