Delirium is a common problem in hospitalized adults with a high degree of associated morbidity, prolonged length of hospital stay, and increased healthcare costs. Currently, there are no interventions approved for the prevention of delirium. Current medical options for managing delirium such as antipsychotic drugs are associated with their own morbidity, including cardiac arrhythmias and oversedation. Melatonin, a supplement used for sleep with an excellent safety profile, may have the potential to dramatically decrease rates of delirium in hospitalized adults. Direct benefits for patients in our study are unknown and subjects may not directly benefit from participation.

SECTION X: RESEARCH ALTERNATIVES AND ECONOMIC CONSIDERATIONS

1. **Alternatives:** What other alternatives are available to the study subjects outside of the research?

Not to participate in the study.

2. **Payments for Participation (Economic Considerations):** Describe any payments that will be made to subjects, the amount and schedule of payments, and the conditions for receiving this compensation.

None

3. **Costs for Participation (Economic Considerations):** Clearly describe the subject's costs associated with participation in the research, and the interventions or procedures of the study that will be provided at no cost to subjects.

None

4. **In Case of Injury:** This section is required for any research involving more than minimal risk.

No more than minimal risk is involved.

- a. Will medical treatment be available if research-related injury occurs?
Yes, during the same hospitalization period.
- c. Where and from whom may treatment be obtained?
From the medical team caring for the patient during the admission.
- d. Are there any limits to the treatment being provided?
We do not expect so, but will defer to the primary medical team caring for the patient.
- e. Who will pay for this treatment?
The patient's insurance company, or the patient.
- f. How will the medical treatment be accessed by subjects?
The medical treatment will be available during the hospitalization, and the PI will notify the primary medical team, as appropriate.

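### The second primary outcome is worded with hospital days as its denominator, while the event rules and the only time-based analysis use days to first delirium; computed as worded, a real benefit is modestly attenuated

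*Combined protocol and SAP*

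**What the plan says.** All references are to the combined protocol and SAP.

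- Section V.12 (Statistical Considerations) lists two primary outcomes: "Incidence of delirium per admission of medical geriatric patients" and "Incidence of delirium per patient days of hospitalization in medical admission of geriatric patients". It does not define the days in the second, and it names no rate model for it.
- Section V.3 (Research Plan) defines the endpoint as "occurrence of delirium as defined by the Short CAM by the time of discharge or prior to hospital day 15". It adds: "If the primary end point of delirium is reached, the subject will have completed the study, participation will be over". Each subject can therefore contribute at most one event.
- Section V.12 gives one time-based analysis: "Person days to delirium will be compared between the two groups using Survival analysis with Kaplan Meier curves, logrank test and Cox proportional hazards". That clock stops at delirium. The text does not say that this analysis belongs to the second primary outcome.
- Section IX (Potential Benefits) describes delirium as a problem "with a high degree of associated morbidity, prolonged length of hospital stay, and increased healthcare costs", with no figure in days.
- Section VIII, item a, includes admission date, length of stay and the daily CAM result among the information to be collected.

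**The concern.** A rate needs a denominator made of time in which a counted event could occur. Here a subject is out of the risk set once delirium is recorded, and nothing counts from hospital day 15. Total days in hospital include time after both points, as well as the short period on the floor before randomisation.

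The days after onset matter most because they depend on the outcome. If delirious patients stay longer, the arm with more delirium collects more denominator days, which lowers its rate. The rate ratio then mixes the effect of melatonin on delirium with the relation between delirium and stay. An analyst who follows the listed wording would report a weaker effect for a primary outcome than the survival analysis of the same events shows, and the plan would not say which result stands.

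**Working it through.** **Inputs from Section V.12.** Control incidence 30%, melatonin incidence 21% (risk ratio 0.70), two-sided 5% level, 80% power, 1:1 allocation, 367 per arm.

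**Plan's own figure.** The two-proportion formula without continuity correction, with mean proportion 0.255, is

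n = [1.960 × √(2 × 0.255 × 0.745) + 0.842 × √(0.30 × 0.70 + 0.21 × 0.79)]² / 0.09² = 367 per arm, or 734 in total.

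This matches the plan. The size rests on the proportion per admission, so the choice of days does not enter it.

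**Assumed inputs (not in the documents).** S = mean stay without delirium; t = mean day of onset; D = mean total stay of a delirious subject; x = D − S. All are taken as equal in the two arms.

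**Formulas.** For incidence p, events per patient-day are:

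- at risk: p / [(1 − p)S + p·t]
- hospital days: p / [(1 − p)S + p·D]

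**Example with S = 5 and t = 3.**

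| Denominator | Melatonin rate | Control rate | Ratio |
|---|---|---|---|
| Days at risk | 0.21/(3.95 + 0.63) = 0.0459 | 0.30/(3.50 + 0.90) = 0.0682 | 0.672 |
| Hospital days, D = 5 | 0.21/5.00 = 0.0420 | 0.30/5.00 = 0.0600 | 0.700 |
| Hospital days, D = 7 | 0.21/(3.95 + 1.47) = 0.0387 | 0.30/(3.50 + 2.10) = 0.0536 | 0.723 |
| Hospital days, D = 8 | 0.21/(3.95 + 1.68) = 0.0373 | 0.30/(3.50 + 2.40) = 0.0508 | 0.734 |
| Hospital days, D = 10 | 0.21/(3.95 + 2.10) = 0.0347 | 0.30/(3.50 + 3.00) = 0.0462 | 0.752 |

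**Range.** Let S run from 4 to 7 days, x from 2 to 5 days, and t be 2 or 3.

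- At risk, the ratio is 0.70 × (0.70S + 0.30t)/(0.79S + 0.21t). It runs from 0.70 × 5.50/5.95 = 0.647 (S = 7, t = 2) to 0.70 × 3.70/3.79 = 0.683 (S = 4, t = 3).
- On hospital days, the ratio is 0.70 × (S + 0.30x)/(S + 0.21x). It runs from 0.70 × 7.60/7.42 = 0.717 (S = 7, x = 2) to 0.70 × 5.50/5.05 = 0.762 (S = 4, x = 5).

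**How much is due to longer stay.** In the example with D = 10, the gap is 0.752 − 0.672 = 0.080. Of this, 0.700 − 0.672 = 0.028, or 35%, is present even when delirium adds no days. That part arises because a rate over equal stays reduces to the risk ratio, whereas a rate over time at risk behaves like a hazard ratio. The remaining 0.052 comes from the longer stay.

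**No effect.** If p is the same in both arms, and S and D are too, the two denominators are equal and the ratio is 1 on either basis.

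**The case against.** The strongest reply is that the plan never says it will compute the attenuated estimate. Section V.12 names no Poisson model and no test on total hospital days. Its one time-based analysis stops at delirium, and the Research Plan ends participation there. On that reading, the survival analysis is simply how the second primary outcome will be analysed, and nothing is biased.

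Much of this stands: the plan already contains the right analysis. But it does not tie that analysis to the outcome, and the listed wording names hospital days without restricting them to time at risk. Full-stay days would also be at hand, because length of stay is a secondary outcome. A primary outcome should not leave this choice to the analyst.

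A reader might also infer from the Section VIII list, which has length of stay but no separate onset date, that the data collection pushes the rate toward total stay. The documents do not support that. The list includes the daily CAM result, from which the first positive day can be derived, and both the duration of delirium and the survival analysis need onset in any case.

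The remaining objections concern size and hold. Section IX states an association with no number of days, and doubling the stay is the high end of the worked example. Time before randomisation is limited by the 24-hour consent window and balanced by randomisation.

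**Conclusion.** The point holds as a mismatch between the wording of a primary outcome and both the event rules and the planned time-based analysis. If the rate is computed as worded and melatonin works at the design effect, the ratio is about 0.72 to 0.76 instead of 0.65 to 0.68. Measured against the design risk ratio of 0.70, a doubled stay loses (0.752 − 0.700)/0.300 = 17% of the benefit. These figures rest on assumed stay and onset values; the direction rests on the protocol's own statement that delirium goes with longer stay.

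A reader might infer that the trial's main result will be biased, or that its power or false-positive rate is compromised. The documents do not support that: the per-admission outcome and the 734 sized on it do not use days, the ratio stays at 1 under no effect, and the survival analysis already uses time at risk. The change is worth making because the outcome is labelled primary and the correction is almost free.

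**What to change.** Reword the second primary outcome in Section V.12 as first delirium per patient-day at risk. Count days from randomisation to the earliest of first positive Short CAM, discharge, death or the end of hospital day 14. Use randomisation itself as the start, not the first capsule, so that a positive assessment between the two has a defined place.

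Then state that the Kaplan-Meier, logrank and Cox analyses, run on this same clock, are the analysis of this outcome. Take the day of onset from the CAM results already listed in Section VIII, kept with their dates; discharge follows from admission date and length of stay.

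The cost is two sentences of text. No new data fields, patients or procedures are needed, and the sample size does not change.
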